9.3. Efficacy Analysis

The primary efficacy parameter is ORR by IMWG criteria. The ORR will be evaluated using 2-sided 80% exact binomial confidence intervals. The rate variables such as CR, sCR, nCR, and VGPR will be evaluated using 2-sided 80% exact binomial confidence intervals.

The distribution of time-to-event response including DOR, TOS, PFS, and OS will be estimated by Kaplan-Meier methodology. The medians of these time-to-event efficacy responses, if available, and their 2-sided 95% CI, will be reported. In addition, the proportions of patients with events at selected time points, together with their 2-sided 95% CI will be presented. The calculations will be performed based on a fixed sample, single-stage design. Time to event analysis will be based on all data combined.

Exploratory endpoints including biomarkers, microbiome, blood variables, and exosome will be summarized descriptively.

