This Simon's two-stage design yields a type I error rate of 0.095 and power of 0.802 when the true response rate is 48%. The probability of early stopping due to futility is approximately 49.2%.

Primary Analysis

After a maximally 42 patients are enrolled in the phase 1b and phase 2 portions combined, a primary interim efficacy analysis and the second safety analysis will be conducted. The subset safety analysis will be also descriptively performed based on the previous exposure groups (Dara + Len + Dex or Dara + Pom + Dex).

Overall response rate (ORR) and stringent complete response (sCR)/CR/near CR (nCR) according to IMWG criteria will be determined and corresponding 2-sided 80% exact binomial confidence interval will be calculated. The subset ORR analysis will be also performed based on the previous exposure groups (Dara + Len + Dex or Dara + Pom + Dex).

The Kaplan-Meier (KM) method will be used to estimate the time-to-event endpoints such as time on study (TOS), duration of response (DOR), time to progression (TTP), progression-free survival (PFS) and overall survival (OS) distributions. The subset time-to-endpoint outcome analysis will be also performed using the KM method based on the previous exposure groups (Dara + Len + Dex or Dara + Pom + Dex).

Adverse events and tolerability from all subjects who receive at least one dose of study drug will be evaluated for safety and tolerability. Data will be tabulated to examine the frequency.

Study Sites

1. Hackensack University Medical Center - John Theurer Cancer Center - Hackensack, NJ
2. Georgetown-Lombardi Cancer Center - Washington, DC

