9.2. Sample Size and Power Considerations

Phase 1b of the study will follow a standard 3 + 3 dose escalation design as described in Section 7.4. With two dose levels, the study will need between 3 and 12 patients depending on toxicities. Patients will be considered evaluable in phase 1b for MTD assessment provided that they have not missed any of their doses of ATRA in Cycle 1, or have had a DLT. Patients who are not considered evaluable as defined above will be replaced.

For the phase 2 portion:

Approximately 20 patients who fulfill the eligibility criteria of the protocol will be enrolled. The phase 2 study will use a Simon 2-stage minimax design, whereby 10 patients will be accrued in the first stage, and ORR assessed, before moving to the next stage. If ≥ 3 objective responses are observed in the first stage, the study will proceed to the next stage; and an additional 10 patients will be accrued. If there are 8 or

more responses among the 20 patients, the combination will be declared worthy for further evaluation. The null hypothesis that the true response rate is 25% or less will be tested against a one-sided alternative of 48% or higher at the one-sided type I error of 0.10. This design yields a type I error rate of 0.096 and power of 0.806 when the true response rate is 48%. The probability of early stopping due to futility is approximately 52.0%.

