9.5. Interim analysis

The first efficacy analysis for study futility will be assessed 3 months after 10 subjects are enrolled.

This study uses a Simon 2-stage minimax design. Interim analysis will be performed 3 months after 10 subjects are enrolled. If 2 or fewer of those 10 patients have a response, the study will be discontinued after Part 1 due to futility.

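### The planned 80% interval for the primary ORR ignores the two-stage design and, at exactly the success count, narrowly includes the null that the Simon rule rejects

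*Combined protocol and SAP*

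**What the plan says.** **The test.** Section 9.2 sets a Simon minimax design, "whereby 10 patients will be accrued in the first stage, and ORR assessed, before moving to the next stage". Section 9.5 gives the futility rule: "If 2 or fewer of those 10 patients have a response, the study will be discontinued after Part 1 due to futility". Otherwise "an additional 10 patients will be accrued", and with 8 or "more responses among the 20 patients, the combination will be declared worthy for further evaluation". A null of 25% "will be tested against a one-sided alternative of 48% or higher at the one-sided type I error of 0.10". The Protocol Summary gives a different design: 12 then 28 patients, null 30%, stop at 4 or fewer of 12, success at 12 or more of 28.

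**The estimate.** Section 9.3 says of the primary endpoint: "The ORR will be evaluated using 2-sided 80% exact binomial confidence intervals". The Protocol Summary (Primary Analysis) agrees: a "corresponding 2-sided 80% exact binomial confidence interval will be calculated". Neither place names a two-stage interval, a two-stage p-value or a bias-adjusted estimator. Neither says how to report a result where count and interval disagree.

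**The single-stage sentence.** Section 9.3 also states "The calculations will be performed based on a fixed sample, single-stage design". It stands in the paragraph on Kaplan-Meier medians and time-point proportions, directly before a sentence on time-to-event analysis.

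**The concern.** A two-sided 80% interval is the natural partner of a one-sided 0.10 test, so a reader will expect the two to agree. The Simon cut-off meets 0.10 only because trials stopped at stage 1 cannot count as successes. A fixed-sample interval drops that fact. If the final count lands on the cut-off, the report would declare activity beside an interval that does not exclude the null. The team would then have to choose how to present the primary result after seeing the data.

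**Working it through.** **Inputs.** Sections 9.2 and 9.5: n1 = 10, stop if X1 ≤ 2, n = 20, success if S ≥ 8, p0 = 0.25, p1 = 0.48, one-sided 0.10. Protocol Summary: n1 = 12, n = 28, success if S ≥ 12, p0 = 0.30, printed stop at 4 or fewer. Exact binomial is read as Clopper-Pearson.

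**1. Reproduce the plan's figures.** P(success | p) = Σ over x ≥ 3 of b(x; 10, p) · P(X2 ≥ 8 − x | 10, p). At p = 0.25, terms for x = 3 to 8:

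0.2503×0.0781 + 0.1460×0.2241 + 0.0584×0.4744 + 0.0162×0.7560 + 0.0031×0.9437 + 0.0004×1 ≈ 0.0956 (the rest is negligible).

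| Quantity | Stated in 9.2 | Recomputed |
|---|---|---|
| Type I error | 0.096 | 0.0956 |
| Power at 48% | 0.806 | 0.8059 |
| Early stop at 25% | about 52.0% | 52.6% |

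**2. The planned interval at 8/20.** The lower limit solves P(X ≥ 8 | 20, p) = 0.10 and the upper solves P(X ≤ 8 | 20, p) = 0.10. Result: 24.91% to 56.73%, which includes 25%. The matching single-stage p-value is P(X ≥ 8 | 20, 0.25) = 0.1018, above 0.10. The gap to the two-stage value, 0.1018 − 0.0956 = 0.0062, is the chance of 8 or more by way of a first stage that would have been stopped. At 9/20 the lower limit is 29.29%, so the conflict occurs at 8/20 only.

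**3. The two-stage interval.** Order stopped trials below continuing ones. The lower limit solves P(X1 ≥ 3 and S ≥ 8 | p) = 0.10; the upper solves 1 − P(X1 ≥ 3 and S ≥ 9 | p) = 0.10. Result: 25.24% to 57.09%, which excludes 25%.

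**4. The same at 12/28.**

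| Method | 80% interval | Excludes 30%? |
|---|---|---|
| Planned, fixed sample | 29.87% to 56.67% (p = 0.1028) | No |
| Two-stage, stop at 3/12 | 30.23% to 57.21% | Yes |
| Two-stage, stop at 4/12 as printed | 31.20% to 59.21% | Yes |

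Both stops are shown because the printed 4/12 gives type I error 0.078 and, at 50%, power 0.730. A stop at 3/12 gives 0.095 and 0.802, the figures stated in the Protocol Summary (which labels the power as at 48%).

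**5. How often (10/20 design).** P(stage 1 passed and S = 8) is 5.6% at a true 25%, 14.8% at 35% and 12.7% at 48%. As a share of declared successes that is 58%, 39% and 16%.

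**6. The raw proportion (10/20 design).** Averaged over all outcomes, E = Σ over x ≤ 2 of b(x; 10, p)·x/10 + Σ over x ≥ 3 of b(x; 10, p)·(x + 10p)/20.

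| Mean raw ORR | True 25% | True 48% |
|---|---|---|
| All outcomes | 22.2% | 46.9% |
| Trials reaching stage 2 | 30.9% | 49.1% |
| Declared successes | 43.1% | 51.7% |

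The UMVUE at S = 8 is Σ C(9, x−1)·C(10, 8−x) / Σ C(10, x)·C(10, 8−x), x = 3 to 8: 48,378 / 115,275 = 42.0%, against a raw 40.0%.

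**7. Coverage of the planned interval (10/20 design).** It is 86% to 93% at true rates of 20% to 40%, but 78.5% at the design alternative of 48%. There the lower limit lies above the truth 9.7% of the time, so the upper limit falls below it 100 − 78.5 − 9.7 = 11.8% of the time.

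**The case against.** The strongest reply is that nothing turns on this. Success is defined by the response count, no section uses the interval as a test, and the Simon error rates hold whichever interval is printed. That stands. A reader might infer that the plan could reach a wrong go/no-go decision or exceed its type I error; the documents do not support that.

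The conflict is also tiny: 24.9% against 25% at one count, with an interval about 32 points wide, and it vanishes if limits are rounded to whole percents. That stands too. At the rates checked, the planned lower limit exceeded the truth at most 9.7% of the time, so it errs on the cautious side. The shortfall at 48% is on the upper side.

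Two stronger readings fail. One is that the single-stage sentence commits the ORR analysis to a single-stage method. Its position points to time-to-event endpoints, and its scope is at best ambiguous. The point does not need it, because the two ORR sentences already specify a plain exact interval. The other is that the raw ORR is biased low in a trial that reports success. The low bias holds only when early stops are averaged in; among trials reaching stage 2, and among successes, the raw figure runs high.

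Finally, Section 9.1 leaves detailed methods to a statistical analysis plan, so this could be called missing detail. That stands only in part: for the ORR interval the plan does name a method, and that method does not match its own test.

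**Conclusion.** The mismatch is real but small. The planned interval contradicts the Simon result only at the exact cut-off: by 0.1 point at 8/20 (24.9% against 25%) and 0.1 point at 12/28 (29.9% against 30%). A two-stage interval removes the conflict under either design. The cut-off is a realistic outcome, with a probability of about 6% to 15% at the true rates shown for the 10/20 design. The decision rule is untouched. The bias of the raw proportion is 1 to 3 points low unconditionally (10/20 design), and its direction reverses once the trial passes stage 1.

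This rests on four assumptions: exact binomial means Clopper-Pearson; the point estimate, which the plan does not name, is the sample proportion; limits are shown to at least one decimal; and ORR is computed on the Simon-tested patients. The last is unsettled, because the Protocol Summary describes a primary analysis after up to 42 patients from both phases. With a denominator other than 20 or 28, these threshold figures do not apply.

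**What to change.** First settle which Simon design governs (10/20 or 12/28, with its stage 1 rule) and which patients it is applied to; a two-stage interval cannot be specified until then. Then, in Section 9.3 and the Protocol Summary:

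- State that the primary ORR among the Simon-tested patients is reported with a two-stage exact 80% interval (stage-wise ordering) matched to that design, with the UMVUE beside the raw proportion.
- State that the single-stage sentence applies only to endpoints not tested by the Simon rule.

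The cost is a sentence or two and a few lines of code, with no added patients and no change to the decision rule. The downside is slightly more analysis work and an interval that is less familiar to clinical readers.

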9.4. Safety analysis

All safety analyses will be performed on subjects who take at least one dose of study treatment and summarized using descriptive statistics. A separate listing and summary of all AEs and SAEs will be provided.

Please refer to Section 7.4 regarding stopping rules for dose-escalation during Phase 1b.

For phase 2, the first safety analysis will be performed 3 months after the first 10 patients are enrolled and the second safety analysis will be performed 3 months after the next 10 patients are enrolled.

A threshold of fatal AEs related to ATRA of <10% is proposed. Any rate of fatal events related to ATRA clearly in excess of this will result in stopping of the trial. For the 20 patients expected to be treated between phase 1b and phase 2 with one specific dose, this means that the cohort will be stopped if 1 or more fatal TEAEs occur during the first stage of phase 2, and 2 or more fatal TEAEs occur in both stages.

This trial will also be stopped if the rate of TEAE, Grade 4 events, in any non-hematologic system organ class (SOC) exceeds 10% with the exception of Grade 4 asymptomatic laboratory abnormalities. This trial will also be stopped if events meeting the criteria of a DLT occur with an incidence of >40% at any point. The stop will result in an immediate halt in enrollment and may also necessitate the halting of treatment of ongoing patients, depending on the nature and severity of the safety data by the investigators.

The All-Subjects-as-Treated (ASaT) population will be employed for safety analyses. The ASaT population consists of all subjects who received at least one dose of trial treatment. Subjects who entered the study and did not take any of the study drug(s) and had this confirmed, will not be evaluated for safety.

Descriptive tables that summarize the number and percentage of subjects that experience adverse events as categorized in the NCI CTCAE Version 5 will be generated:

The severity of the toxicities will be graded according to the NCI CTCAE v5 whenever possible.

Of note, a death from an unrelated and unforeseen circumstance (i.e. car accident) will not be counted toward toxicity for the stopping rules.

A grade 3 unexpected AE in the first patient will not stop enrollment in the arm

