4. OVERALL STUDY DESIGN

4.1. Study Design

This is a multicenter, open label study of Dara+Pom+Dex combined with ATRA in patients progressing on a Dara+Len+Dex regimen. The study is expected to enroll up-to a maximum of 42 patients (20-32 subjects previously exposed to Dara + Len + Dex; 10-22 subjects previously exposed to Dara + Pom + Dex)..

The phase 1b portion will follow a standard 3+3 dose escalation design with two dose levels and up to 12 patients. Under this design, the investigators will evaluate dose levels as follows:

- Dose level 1 - ATRA 35.5 mg/m²/day on days -2,-1 and 1 on a 28-day cycle in combination with daratumumab, pomalidomide, and dexamethasone
- Dose level 2 – ATRA 45 mg/m²/day on days -2,-1 and 1 on a 28-day cycle in combination with daratumumab, pomalidomide, and dexamethasone

During the dose-escalation phase and after the first cycle, and after the first cycle, patients who have not experienced a DLT, have not shown signs of PD, and in the opinion of the investigator would continue to benefit from treatment may receive additional cycles of treatment.

The phase 2 portion will be conducted in two stages. In the first stage, 10 patients will be accrued. A safety and efficacy analysis will be conducted 3 months after accrual of the first 10 patients. If there are 2 or fewer responses in these 10 patients, the study will be stopped due to futility. If the stopping rules for safety are met, then the study will be stopped due to toxicities. Otherwise, accrual will continue for a maximum of 42 in phase 1b and phase II combined.

During 28-day treatment cycles, patients will receive Dara 1800 mg subcutaneous (SC) at their current dose upon enrollment onto the study depending on their cycle. (If they are on cycles 1-2 then they will receive Dara 1800 mg SC days 1,8,15,22; if they are on cycles 3-6 they will receive Dara 1800 mg SC days 1 and 15; if they are on cycle 7 or beyond they will receive Dara 1800 mg SC on day 1).

Pomalidomide will be administered at the patient's currently tolerated dose (4,3, or 2 mg po daily) on days 1-21. For patients progressing on daratumumab, lenalidomide, and dexamethasone, the starting dose of pomalidomide will be 4 mg per standard of care.

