10.3.1. Causality

The investigator must determine the relationship between the administration of IPs (POM, DARA, or LD-Dex) and the occurrence of an AE/SAE as Not Suspected or Suspected as defined below:

Not suspected: Means a causal relationship of the adverse event to IP (POM, DARA, or LD-Dex) administration is unlikely or remote, or other medications, therapeutic interventions, or underlying conditions provide a sufficient explanation for the observed event.

Suspected: Means there is a reasonable possibility that the administration of IP (POM, DARA, or LD-Dex) caused the adverse event.

‘Reasonable possibility’ means there is evidence to suggest a causal relationship between the IP and the adverse event.

Causality should be assessed and provided for every AE/SAE based on currently available information. Causality is to be reassessed and provided as additional information becomes available.

If an event is assessed as suspected of being related to a comparator, ancillary, or additional IP that has not been manufactured or provided by Janssen, please provide the name of the manufacturer when reporting the event.

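### The fatal-event stopping rule in Section 9.4 turns on relation to ATRA, which the causality section does not ask investigators to assess, and its wording leaves open when the rule fires

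*Combined protocol and SAP*

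**What the plan says.** Section 9.4 states the fatal-event rule in three steps.

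- The limit: "A threshold of fatal AEs related to ATRA of <10% is proposed".
- The consequence: "Any rate of fatal events related to ATRA clearly in excess of this will result in stopping of the trial".
- The counts, introduced as the meaning of the above: "For the 20 patients expected to be treated between phase 1b and phase 2 with one specific dose", the cohort stops if "1 or more fatal TEAEs occur during the first stage of phase 2, and 2 or more fatal TEAEs occur in both stages".

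The only stated exemption is that "a death from an unrelated and unforeseen circumstance (i.e. car accident) will not be counted toward toxicity for the stopping rules". Section 4.1 makes the consequence firm: "If the stopping rules for safety are met, then the study will be stopped due to toxicities".

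Attribution is covered in Section 10.3.1: "The investigator must determine the relationship between the administration of IPs (POM, DARA, or LD-Dex) and the occurrence of an AE/SAE". An event may be classed as not suspected when "other medications, therapeutic interventions, or underlying conditions provide a sufficient explanation for the observed event". Sections 5.2, 10.1, 10.3.3, 10.3.5 and 10.10 repeat the three-drug list, and Section 7.8 uses it for compliance. ATRA is not named anywhere in Section 10.

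**The concern.** ATRA is the drug added to the regimen, the only one being dose-escalated, and the subject of the fatal-event rule. A rule about ATRA-related deaths needs someone to record whether each death was related to ATRA, and the written causality procedure does not ask for that.

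The rule can also be read in more than one way at the moment it matters. After a single stage 1 death, the count says stop, while the sentence about a rate clearly above 10% gives grounds to continue. It is not explicit whether that death must be ATRA-related, or whether the second count must also be met. Two careful people could reach different decisions on the same death.

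**Working it through.** **1. Attribution, section against section**

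- Section 9.4 needs relation to ATRA.
- Section 10.3.1 assesses pomalidomide, daratumumab and dexamethasone. ATRA is off that list, so it can be taken as one of the other medications. A death it fully explains may then be coded as not suspected.
- Sections 5.2, 10.1 and 10.10 require all SAEs up to at least 30 days after treatment, whatever the cause. After that they require only SAEs suspected to be related to the three listed drugs. A late SAE suspected to be due to ATRA alone is outside that duty.
- Section 10.3.1 also mentions an additional IP not supplied by the daratumumab manufacturer. It asks only for a manufacturer's name once an event is already suspected.

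**2. The counts against the limit**

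Inputs: stages of 10 + 10 (Section 9.2); counts of 1 and 2 (Section 9.4); stages of 12 + 16 = 28 (Protocol Summary, Statistical Considerations).

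- Body-text sizes: 1/10 = 10.0% and 2/20 = 10.0%. The next lower counts give 0/10 = 0% and 1/20 = 5%. So 1 and 2 are the smallest counts not below 10%, and the plan's counts reproduce its limit.
- An observed rate actually above 10% would need 2/10 = 20% and 3/20 = 15%.
- Clearly above 10% is undefined. If it is taken to mean an exact one-sided lower confidence limit above 10% (my assumption), the counts are 3/10 and 4/20 at 80% confidence, 3/10 and 5/20 at 90%, and 4/10 and 5/20 at 95%.
- Summary sizes: 1/12 = 8.3% and 2/28 = 7.1%, both below the limit.
- If 6 phase 1b patients at the dose are added to 20 phase 2 patients: 2/26 = 7.7%.

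**3. 'And' or 'or'**

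Let X1 and X2 be independent Bin(10, p), where p is the true rate of countable fatal events. The documents give no rate, so 2%, 5% and 10% are assumptions.

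- Counts as alternatives: P(X1 ≥ 1) + P(X1 = 0) × P(X2 ≥ 2)
- Both required: P(X1 + X2 ≥ 2) − P(X1 = 0) × P(X2 ≥ 2)

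| p | P(X1 ≥ 1) | P(X1 = 0) × P(X2 ≥ 2) | P(X1 + X2 ≥ 2) | Alternatives | Both required |
|---|---|---|---|---|---|
| 2% | 0.183 | 0.817 × 0.016 = 0.013 | 0.060 | 0.196 | 0.047 |
| 5% | 0.401 | 0.599 × 0.086 = 0.052 | 0.264 | 0.453 | 0.213 |
| 10% | 0.651 | 0.349 × 0.264 = 0.092 | 0.608 | 0.743 | 0.516 |

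For comparison, alternatives set strictly above 10% (2 of 10, or 3 of 20) stop with probability 0.12 at p = 5% and 0.39 at p = 10%.

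**4. Which deaths count**

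The limit and its consequence speak of ATRA-related deaths. The counts speak of fatal TEAEs and exclude only deaths that are both unrelated and unforeseen. That exclusion would be largely unnecessary if only ATRA-related deaths counted, so the text supports either reading.

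**The case against.** Several points on the other side stand.

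- A reader might infer that the counts contradict the 10% limit. They do not: 10% is not below 10%, and the counts are the smallest that reach it. The conflict is only with the clearly-in-excess wording, and it can be argued that the explicit, more cautious counts already resolve it.
- The phrase linking the counts to the preceding sentences may carry the ATRA condition over. If so, the missing condition is a drafting point, but the rule then depends wholly on an attribution that Section 10.3.1 does not request. If not, nearly every fatal TEAE counts and the rule itself needs little ATRA attribution. The documents support an ambiguity, not both defects at full weight.
- A reader might infer that ATRA deaths would go unseen. The documents do not support that. Section 10.6 makes every death an SAE, all SAEs are reportable to at least 30 days, and Section 11.3 provides continuous review by the study team, quarterly committee review and reporting of all SAEs to the IRB.
- A reader might infer that relation to ATRA is never judged. Sections 7.5 and 7.6 expect such judgements for dosing, and the eCRF is not among the documents, so an ATRA field may exist. The silence in Section 10.8, which covers reporting to the daratumumab manufacturer, is unremarkable.
- The stopping probabilities rest on assumed rates. They show that the readings differ in practice; they do not show that the rule is too strict.

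What remains is that the sections governing causality and late SAE reporting omit the drug the rule names. The additional-IP sentence does not fill that gap, and committee review does not supply the attribution.

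**Conclusion.** The point holds in a limited form and should be fixed. As written, a death explained by ATRA alone can be classed as not suspected, and a late SAE suspected to be due to ATRA alone lies outside the post-30-day duty. The gap is in required attribution and late reporting, not in capture of deaths.

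Separately, Section 9.4 does not give one rule. With stages of 10 and 20, one stage 1 death meets the count at exactly 10%, while a rate above 10% needs two, and a rate clearly above it needs three or four under the confidence limits assumed here. Reading 'and' literally lowers the stopping probability from 45% to 21% at an assumed 5% rate (20% to 5% at 2%; 74% to 52% at 10%). These figures assume independent patients, 10 per stage, and no phase 1b patients in the count. Agreement between counts and limit also depends on those sizes; it fails with 12 and 28.

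**What to change.** **Attribution.** Add ATRA to the drugs named in Sections 10.3.1, 5.2, 10.1 and 10.10 and, for consistency, in 10.3.3, 10.3.5 and 7.8. Keep the existing Section 10.3.1 definition of a suspected relation; a new causality standard is not needed and could narrow the rule.

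**Stopping rule (Section 9.4).**

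- Replace the clearly-in-excess wording with 'not below this', which matches the limit and the counts.
- Join the two counts with 'or', and record that this changes the current text.
- State which deaths count. One option is all fatal TEAEs except unrelated and unforeseen ones, the more cautious reading of the present counts. The other is only those with a suspected relation to ATRA, alone or with other study drugs.
- State whether phase 1b patients at the dose are among the 20.
- Align the counts with the stage sizes finally used. At 12 and 28, the smallest counts not below 10% are 2/12 = 16.7% and 3/28 = 10.7%. If 1 and 2 are kept there, say that the rule deliberately fires below 10%.

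**Cost.** Protocol wording, plus an ATRA causality field on the eCRF if there is none; no extra patients or procedures. The rule's strictness becomes explicit (45% stopping at an assumed 5% rate with 10 + 10), and the sponsor may have to justify it.

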10.3. Severity / Intensity

For both AEs and SAEs, the investigator must assess the severity / intensity of the event.

The severity of AEs will be graded based upon the subject's symptoms according to the National Cancer Institute (NCI) Common Terminology Criteria for Adverse Events (CTCAE, Version 5);

https://ctep.cancer.gov/protocoldevelopment/electronic_applications/docs/CTCAE_v5_Quick_Reference_8.5x11.pdf

Adverse events that are not defined in the NCI CTCAE should be evaluated for severity according to the following scale:

- Grade 1 = Mild – transient or mild discomfort; no limitation in activity; no medical intervention/therapy required
- Grade 2 = Moderate – mild to moderate limitation in activity, some assistance may be needed; no or minimal medical intervention/therapy required
- Grade 3 = Severe – marked limitation in activity, some assistance usually required; medical intervention/therapy required, hospitalization is possible
- Grade 4 = Life threatening – extreme limitation in activity, significant assistance required; significant medical intervention/therapy required, hospitalization or hospice care probable
- Grade 5 = Death – the event results in death

The term “severe” is often used to describe the intensity of a specific event (as in mild, moderate, or severe myocardial infarction); the event itself, however, may be of relatively minor medical significance (such as severe headache). This criterion is not the same as “serious” which is based on subject/event outcome or action criteria associated with events that pose a threat to a subject’s life or functioning.

Seriousness, not severity, serves as a guide for defining regulatory obligations.

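### The 10% organ-class stop in Section 9.4 counts Grade 4 only, so one second-stage death in place of a third Grade 4 case can remove a stop

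*Combined protocol and SAP*

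**What the plan says.** Section 9.4 sets three phase 2 safety stops.

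- **Organ-class rule:** "This trial will also be stopped if the rate of TEAE, Grade 4 events, in any non-hematologic system organ class (SOC) exceeds 10" per cent. Asymptomatic Grade 4 laboratory abnormalities are excepted. No counts are given, nor is a denominator, and the rule does not say whether it counts patients or events.
- **Fatal-event rule:** "A threshold of fatal AEs related to ATRA of <10% is proposed". This becomes counts with the words "For the 20 patients expected to be treated between phase 1b and phase 2 with one specific dose": the cohort is "stopped if 1 or more fatal TEAEs occur during the first stage of phase 2", or if "2 or more fatal TEAEs occur in both stages".
- **DLT rule:** stop if the incidence of DLT-type events is above 40%.

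Deaths from unrelated and unforeseen causes are left out of the stopping rules. On timing, "the first safety analysis will be performed 3 months after the first 10 patients are enrolled", and a second analysis follows after the next 10.

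On grading, Section 9.4 says "The severity of the toxicities will be graded according to the NCI CTCAE v5 whenever possible". The scale written out in Section 10.3, for events that CTCAE does not define, lists "Grade 5 = Death – the event results in death" as a grade above Grade 4. Where the protocol means a grade and everything above it, it uses the ≥ sign, as in the DLT definition (7.3) and the events of special interest (10.4). The causality assessment in 10.3.1 names pomalidomide, daratumumab and dexamethasone, but not ATRA.

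**The concern.** A safety boundary should become easier to cross as outcomes get worse. Read literally, the organ-class rule does not behave this way. A patient with a life-threatening event who survives adds one to the numerator. If the same patient dies, the event becomes Grade 5 and, counted at worst grade, no longer adds to it. If no other rule picks up that death, the trial continues with data that would have stopped it had the patient lived.

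The fatal-event rule is meant to pick up deaths, but its threshold sentence refers to deaths related to ATRA while its counts refer to fatal TEAEs without attribution. How much of the gap it closes depends on which wording governs. Two people applying Section 9.4 to the same data could therefore disagree on whether the trial must stop.

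**Working it through.** **Inputs from the document.** Looks at 10 and 20 patients (9.4); organ-class limit above 10%; fatal-event counts of 1 in the first stage and 2 over both stages; DLT limit above 40%.

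**Assumptions.** Events are counted per patient at worst grade; the denominator is the 10 and then 20 patients of the two looks; CTCAE-graded deaths are Grade 5, as on the 10.3 scale; all events considered fall in one organ class. The Grade 4 and Grade 5 rates below are not in the document.

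**1. The plan's own counts.** The smallest count whose rate is not below 10% is 1 of 10 and 2 of 20. This reproduces the stated fatal-event counts.

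**2. Organ-class counts.** Above 10% means at least 2 of 10 (1/10 is exactly 10%) and at least 3 of 20 (2/20 is exactly 10%). The DLT rule needs at least 9 of 20 (8/20 is exactly 40%).

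**3. The reversal at 20 patients.**

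| One organ class, no first-stage death | Grade 4 rate | Fatal count | Result |
|---|---|---|---|
| 3 Grade 4 | 3/20 = 15% | 0 | stop |
| 2 Grade 4 + 1 second-stage death | 2/20 = 10% | 1 (below 2) | no stop |
| Same, with Grade 5 counted | 3/20 = 15% | 1 | stop |

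The DLT rule does not help, since 3 events are fewer than 9. Enumerating all combinations, this is the only configuration missed when every fatal TEAE counts under the fatal-event rule. At 10 patients, 1 Grade 4 plus 1 death gives 1/10 = 10% and no organ-class stop, but the fatal-event rule stops the trial if it counts that death.

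**4. Size if every fatal TEAE counts.** The missed case needs no first-stage death, one second-stage death, and two Grade 4 patients of whom at most one is in the first stage. Write P(a,c) for the multinomial probability of a Grade 4 and c Grade 5 patients in 10. With rates of 10% and 5%:

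- P(0,0) = 0.85^10 = 0.1969
- P(2,1) = 360 × 0.10² × 0.05 × 0.85^7 = 0.0577
- P(1,0) = 10 × 0.10 × 0.85^9 = 0.2316
- P(1,1) = 90 × 0.10 × 0.05 × 0.85^8 = 0.1226

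Loss = 0.1969 × 0.0577 + 0.2316 × 0.1226 = 0.0398. Stopping probability is 67.9% as written and 71.8% with Grade 5 counted.

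**5. Size if none of the deaths falls under the fatal-event rule.** With X1 and X2 the counts in each 10, P(stop) = 1 − [P(X1=0)·P(X2≤2) + P(X1=1)·P(X2≤1)].

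- Grade 4 only, rate 10%: 1 − (0.3487 × 0.9298 + 0.3874 × 0.7361) = 39.1%
- Grade 4 or 5, rate 15%: 1 − (0.1969 × 0.8202 + 0.3474 × 0.5443) = 64.9%

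**6. Range over assumed rates** (as written → Grade 5 counted).

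| Grade 4 / Grade 5 | All fatal TEAEs count | No death counts |
|---|---|---|
| 5% / 2% | 29.5 → 31.4% (1.8 points) | 12.0 → 22.1% (10.1) |
| 5% / 5% | 52.4 → 55.0% (2.6) | 12.0 → 39.1% (27.0) |
| 10% / 5% | 67.9 → 71.8% (4.0) | 39.1 → 64.9% (25.9) |
| 15% / 2% | 72.5 → 74.9% (2.4) | 64.9 → 73.1% (8.1) |
| 15% / 5% | 82.2 → 85.4% (3.2) | 64.9 → 82.6% (17.7) |

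Inside the range the right-hand loss peaks slightly higher, at about 28 points near 7% and 5%.

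**7. Other denominators.** The synopsis has stages of 12 and 28, and total enrolment is capped at 42. The smallest counts above 10% become 2 of 12, 3 of 28 and 5 of 42. The numbers move, but the mechanism does not.

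**The case against.** The strongest reply is that fatal events have their own rule, placed just before this one, which works across all organ classes and is tighter in the first stage. This largely stands: if every fatal TEAE counts, only a lone second-stage death escapes.

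A reader might infer instead that deaths attributed to the backbone drugs escape every rule, and so take the fall from 65% to 39% in stopping probability as the size of the problem. The document does not establish that reading. The operative counts say fatal TEAEs with no attribution. Section 9.4 then excludes only unrelated and unforeseen deaths, an exclusion that would be largely redundant if only ATRA-related deaths counted. Section 10.3.1 does not ask for causality to ATRA at all. The threshold sentence does say related to ATRA, however, so the narrower reading cannot be ruled out.

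It can also be said that the patient need not leave the numerator: if a Grade 4 episode before death is tallied as its own event, the patient still counts. Section 9.4 is silent, so the reversal depends on worst-grade counting.

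Finally, every death is a reportable SAE, the study team monitors in real time and the data and safety monitoring committee reviews quarterly (10.6, 10.10, 11.3). A second-stage death would not go unseen. That tempers the consequence, but it does not make the numeric rule coherent.

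**Conclusion.** The concern holds in a limited form. As worded, and counted at worst grade over 20 patients, the organ-class rule can stop the trial for three Grade 4 survivors and let it continue when one of the three dies in the second stage. The reversal needs no assumed event rates.

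Its practical size does need them. It is about 2 to 4 percentage points of stopping probability if all fatal TEAEs count under the fatal-event rule, which is the better supported reading. If that rule is confined to ATRA-related deaths it is about 8 to 27 points at the corners of the assumed range. That second figure is an upper bound, because it takes no death to be attributed to ATRA.

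The document does not support the broader claim that fatal toxicity goes unguarded. A counted first-stage death, or two counted deaths over both stages, stops the trial. This is a cheap correction worth making, together with reconciling the two descriptions of which deaths count.

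**What to change.** In Section 9.4:

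- Define the organ-class numerator as patients whose worst grade in that organ class is 4 or higher, Grade 5 included. This also settles the unit as patients, which the present wording leaves open.
- State the denominator at each look.
- Keep the 10% threshold, the asymptomatic-laboratory exception and the exclusion of unrelated, unforeseen deaths.
- State whether the fatal-event rule counts all fatal TEAEs or only those related to ATRA. If the latter, the causality assessment in 10.3.1 must cover ATRA.

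The text change is a few words. The cost is a higher chance of a safety halt, including when the true rate is under the limit. At an assumed 5% Grade 4 and 2% Grade 5 (7% combined), that chance rises from 29.5% to 31.4% if all fatal TEAEs already count. It rises from 12.0% to 22.1% if no death falls under the fatal-event rule. The cost should be judged after the sponsor settles which deaths count.
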